The objective of this study is to develop a brief, culturally sensitive face-to-face smoking cessation intervention for Hispanic construction workers and conduct a pilot two-arm, cluster-randomized clinical trial (RCT) to test the developed intervention for acceptability and potential efficacy- A two-arm, cluster-randomized controlled trial will be conducted with at least 14 construction sites (dependent on how many smokers can be recruited from each site), selected from one Construction Company in south Florida. Cluster randomization is used with construction site chosen as the unit of allocation because it is most practical in this setting and minimizes the risk of spillover effects from the intervention to the control group. Computer-generated random selection will be used to randomize construction sites. Then, construction sites will be randomly assigned to the intervention (enhanced care) or the control group (usual care), and study participants working in these sites will receive treatment accordingly. In conjunction with the site safety manager, we will recruit at least 126 adult Hispanic construction workers who smoke ≥ 5 cigarettes/day. Participants in the enhanced care will receive one culturally adapted brief face-to-face behavioral counseling session developed in phase 1 and delivered during breaks, two brief follow-up phone counseling calls, fax referral to the Florida quitline (QL), and provision of up to 8 weeks of free NRT. Participants in the usual care will receive fax referral to the Florida QL, and provision of up to 8 weeks of free NRT. *Main outcomes* include: 1) estimating yield (number of workers available divided by number eligible; and number eligible divided by number randomized), 2) facilitators and barriers to delivering the intervention in the proposed setting, 3) willingness of participants to be randomized and acceptability of the intervention, 4) follow-up rates, response rates to questionnaires, adherence/compliance rates, and the time needed to collect and analyze data, 5) QL enrollment rates, and 6) exploring the willingness of the target population in involving in the research design and conduct. *Potential efficacy* outcomes include the difference in prolonged abstinence, and point-prevalence abstinence rates at 6-month follow up confirmed by saliva cotinine $< 15\text{ng/ml}$.

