Recruitment, Study Participants, and Procedures- Our target sample size is up to 150 Hispanic smokers. We will coordinate with the safety managers of the participating construction sites to identify smokers who are interested in quitting smoking and arrange a visit to meet these workers. On day 1, two bilingual PH graduate assistants will approach these workers during their break to explain the study, complete the screening, and then obtain the consent form from those who are eligible. To participate in the study participant should be Hispanic male construction workers on site who are \geq 18 year old and have smoked \geq 5 cigarettes/day in the past year. Additionally, potential participants need to be available on site in the following two days, have access to telephone, have no plans to move in the next six months, and be interested in making a serious quit attempt in the next 30 days, and have no contraindication to NRT. Exhaled carbon monoxide levels and saliva cotinine will be tested among eligible participants to verify the self-reported smoking status. Individuals who decline to participate or who are ineligible (e.g., non-Hispanics, women) will be referred to the QL and provided with brochures that include information about the QL contact number and services. They will also be given a flyer about the UM Quitville smoking cessation study for which they may be eligible (only for English speakers). Those who are potentially eligible and interested in participating in the study will sign a consent form, then undergo a baseline screening to confirm eligibility and to collect information about: demographics, job characteristics, acculturation,⁴¹ smoking history, nicotine dependence,⁴² stages of change,⁴³ quit ladder,⁴⁴ smoking self-efficacy,⁴⁵ depression,⁴⁶ social support,⁴⁷ exposure to secondhand smoke, and quality of life. All questionnaires, informed consent, and educational materials will be available in English and Spanish and will be administrated by the bilingual graduate assistants. After completing the baseline assessment, a second visit in the following day will be scheduled to provide the intervention. If time does not permit to complete the entire baseline assessment, the exhaled carbon monoxide and saliva cotinine test, demographics and smoking behavior questions will be administered on-site and the remainder will be given to the

STUDY PROTOCOL AND ANALYSIS PLAN

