disqualified from the study if they report a history of hypersensitivity to nicotine, recent (past month) myocardial infarction, or any history of serious arrhythmias or unstable angina pectoris, consistent with Clinical Practice Guidelines. In addition, individuals will not be eligible if they have a generalized chronic dermatological disorder (e.g. psoriasis), a contraindication for patch use, unless they are able to use nicotine gum. If there are no contraindications, participants will be given their preferred form and will be provided information on the side effects and proper use. Concomitant smoking and NRT use, as well as use of additional prescription and/or OTC NRT or cessation drugs (e.g., bupropion) will be tested at recruitment, and 3- and 6- month follow ups.

Follow-up and Retention- Participants in both arms will receive two follow-up phone calls at 3 and 6 months after enrollment to assess their smoking status. Those who report quitting smoking at 6 months will be visited at a mutually agreed-upon location to obtain a saliva sample to validate their smoking cessation status using saliva cotinine< 15 ng/ml.^{50,51} Saliva samples will be collected using NicAlert™ kits and analyzed by automated gas liquid chromatography using nitrogen-phosphorus detection and structural analogues of cotinine as internal standards.⁵² To increase completion of the 6-month follow-ups, for those participants that we are unable to meet in person we will mail the NicAlert™ kits with instructions on how to complete and mail back to us.

To maintain active participation for the entire length of the study, extensive retention measures will be taken. These include collecting detailed contact information for relatives/friends, who would know the participant's whereabouts, contacting participants with personalized letters/cards, sending out study-relevant information at 3-month, and individual case management. Participants who complete all portions of the intervention will be given a \$50 incentive. Twenty dollars will be provided after completing the first treatment session, and \$30 at the 6-month follow-up assessment.

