- v. Additional measures such as: social support, smoking self-efficacy, nicotine dependence FTND, stages of change, quit ladder, exposure to secondhand smoke, and Hatsukami withdrawal scale will be also collected.
- vi. Medication Side Effects, Adverse Events and Participant Adherence: These will all be monitored on study participants throughout the study. These will be reported to the study's PI and co-investigators for appropriate follow-up.
- vii. Concomitant Medication Use or Behavior Therapy During Follow-up Visits: The use of additional gum, patch, nicotine nasal spray, inhaler or lozenge, or antidepressants prescribed for smoking cessation will be monitored as they can affect cessation rates. Participation in additional behavioral cessation programs, will also be carefully tracked for this reason.
- viii. Saliva cotinine: For participants claiming via self-report that they have quit smoking at 6-month follow up, we will obtain biomedical validation using salivary cotinine. The saliva cotinine test is noninvasive with virtually no risks. This involves providing saliva. Participants will be visited at a mutually agreed-upon location to obtain a saliva sample. This procedure will be explained during administration of consent as well as in detail, during the 6- month follow up phone interview. Note that in the event that participants (a) report they are not smoking, but (b) refuse to provide a saliva sample, they will be considered smokers. A monetary incentive of \$30 will be given to participants at 6-month follow-up after completing of the test.

7) Data Management*

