Outcome Measures- This pilot study aims to explore the acceptability potential and efficacy of the developed intervention compared to QL. *Main outcomes* include: 1) estimating yield (number of workers available divided by number eligible; and number eligible divided by number randomized), 2) facilitators and barriers to delivering the intervention in the proposed setting, 3) willingness of participants to be randomized and acceptability of the intervention, 4) follow-up rates and response rates to questionnaires, adherence/compliance rates, and the time needed to collect and analyze data, and 5) exploring the “willingness” of the target population to be involved in the research design and conduct.⁶⁰⁻⁶² *Potential efficacy outcomes* will focus on comparing prolonged abstinence (defined as no smoking, not even a puff, after a grace period of two weeks after quit date), and point-prevalent abstinence (defined as self-report of not smoking in the past 7-days; not even a puff) confirmed

STUDY PROTOCOL AND ANALYSIS PLAN

by saliva cotinine level of <15ng/ml at 6-month between the two study arms. For individuals who do not quit entirely, the decrease in smoking (i.e., cigarettes/day) will be assessed.^{63,64} Relapse is defined as smoking at least once/week on two consecutive weeks.⁶⁵ Secondary outcome measures will focus on differences in stage of change/readiness to quit,⁶⁶ and treatment adherence according to intervention assignment.³⁷

All participant data will be coded with an identification number and only approved personnel will have access to the key linking identification numbers with participant names. Data will be stored and managed in REDCap and accessed only by approved study personnel. Paper interview instruments will be stored in a locked filing cabinet.

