Quality Assurance- Our research team is well versed in quality assurance processes for intervention studies.^{44,45,59} Following the strategy suggested by Sechrest,⁶⁹ evaluation of any treatment program should involve satisfactory answers to three questions: 1) was the intervention both standardized and delivered as intended to the participant? 2) if so, did the participants receive it? and 3) if so, was the intervention efficacious in changing behavior? Sechrest's 3rd question involves the evaluation of outcomes, which is outlined in the Data Analysis section below. However, Sechrest's 1st and 2nd questions address treatment implementation issues. To ensure standardization of intervention content and delivery, we will use standardized treatment manuals/procedures developed particularly for this study. Participants will respond to a brief questionnaire at baseline and the 3- and 6- month follow-up to assess whether key points were learned, including the techniques and information discussed in the intervention sessions. Standard procedures will be used for instrument development, protocol and forms, and data management (e.g. entry, reconciliation, updating, and data security and confidentiality). Additionally, we will audiotape a random sample of 10% of counseling sessions for review and feedback. Participants will be asked for permission to audiotape these selected sessions as part of the consent process.

Data Analysis

The analyses of the outcomes were mainly descriptive. Chi-square tests and between-group t-tests were used to compare between-group differences in baseline characteristics, and indices of treatment implementation, adherence, and retention. Intra-class correlation coefficients were used to adjust for clustering within sites.⁵⁵ This adjustment accounted for within-site clustering of workers characteristics at each of the 17 participating sites in the trial. Chi-square tests were used to compare cessation rates in the two arms. Analyses were performed on an intention-to-treat basis, with individuals with missing outcome data or self-reported abstinence not confirmed by eCO at 6-month follow-up classified as not quit. Logistic regression analyses were conducted to assess baseline predictors of prolonged abstinence at 6-months.

8) Risks to Subjects*

Potential risks and adverse effects of the study medication will be explained to each participant when informed consent is obtained. Each participant will be instructed to

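### The analysis rule confirms 6-month quitting by exhaled CO, but the efficacy outcome is defined by saliva cotinine below 15 ng/ml, and no 6-month CO test is described

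*Combined protocol and SAP*

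**What the plan says.** Saliva cotinine is the 6-month test in four places:

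- The opening objective lists prolonged abstinence and "point-prevalence abstinence rates at 6-month follow up confirmed by saliva cotinine", with a cut-off of 15 ng/ml.
- Section 7, Outcome Measures, gives the same confirmation: "by saliva cotinine level of <15ng/ml at 6-month between the two study arms".
- Section 5, Follow-up and Retention, has self-reported quitters visited at 6 months "to obtain a saliva sample to validate their smoking cessation status using saliva cotinine", again with the 15 ng/ml cut-off. Those who cannot be met in person are sent saliva "kits with instructions on how to complete and mail back to us".
- Section 6, item viii, names salivary cotinine as the 6-month validation, without a cut-off. Of self-reported quitters it says that if they "refuse to provide a saliva sample, they will be considered smokers".

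Section 7, Data Analysis, uses a different test. The intention-to-treat rule there has "individuals with missing outcome data or self-reported abstinence not confirmed by eCO at 6-month follow-up classified as not quit".

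The only other mention of exhaled CO is at recruitment, in section 5: "Exhaled carbon monoxide levels and saliva cotinine will be tested among eligible participants to verify the self-reported smoking status".

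**The concern.** The classification rule decides who counts as a quitter in each arm. It therefore sets both numerators in the chi-square comparison of cessation rates. It also bears on the outcome of the second model: "Logistic regression analyses were conducted to assess baseline predictors of prolonged abstinence at 6-months". If the rule rests on a different test from the one in the outcome definition, the analysis does not estimate the stated outcome, and a reader cannot tell which test lies behind the reported quit rates.

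The Sample Size text says these data will help to estimate the effect size for a full-scale trial. Anyone reusing the quit rates for that purpose needs to know how a quitter was confirmed.

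**Working it through.** The plan gives no figure that depends on this point, so the main check compares the texts.

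**1. Every mention of each test**

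| Place | Test | Time | Cut-off |
|---|---|---|---|
| Opening objective | Saliva cotinine | 6 months | <15 ng/ml |
| Section 5, Recruitment | Exhaled CO and saliva cotinine | Enrolment | None given |
| Section 5, Follow-up and Retention | Saliva cotinine, by visit or mailed kit | 6 months | <15 ng/ml |
| Section 6, item viii | Saliva cotinine; refusal counts as smoking | 6 months | None given |
| Section 7, Outcome Measures | Saliva cotinine | 6 months | <15 ng/ml |
| Section 7, Data Analysis | Exhaled CO | 6 months | None given |

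The last row stands alone. Nothing describes a 6-month CO reading, a threshold for it, or a rule for participants without one. Nothing says that CO replaced cotinine.

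**2. The two rules applied to one participant**

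Take a worker who reports abstinence at 6 months, has cotinine below 15 ng/ml and has no CO reading.

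- Under Outcome Measures he is abstinent.
- Under Data Analysis he is not quit.

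The follow-up procedure collects saliva only, so this describes every cotinine-confirmed quitter followed up exactly as section 5 sets out. For anyone reached only by mail, no breath-test route is described at all.

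**3. Scope of the confirmation**

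In the objective and in Outcome Measures, the confirmation phrase follows point-prevalence abstinence. It can be read as covering that outcome alone or prolonged abstinence as well. This is a lesser point, but the same correction can settle it.

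**4. Scale only**

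Inputs: 63 per arm (section 5, Sample Size); response rates of 10% to 15% in control and 25% in intervention (section 11).

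- Control: 0.10 × 63 = 6.3 and 0.15 × 63 = 9.45, so about 6 to 9 quitters.
- Intervention: 0.25 × 63 = 15.75, so about 16 quitters.
- One person reclassified: 1/63 = 1.59 percentage points in that arm.

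Section 11 appears to rest on seven sites of seven workers per arm, or 49. On that basis the counts are 0.10 × 49 = 4.9 and 0.15 × 49 = 7.35 against 0.25 × 49 = 12.25, and one person is 1/49 = 2.0 points.

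Hypothetical counts out of 63 per arm show how sensitive the comparison is. These are chi-square tests that ignore clustering:

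| Control v intervention quitters | p, uncorrected | p, continuity-corrected |
|---|---|---|
| 6 v 16 | 0.019 | 0.035 |
| 6 v 15 | 0.031 | 0.056 |
| 7 v 16 | 0.038 | 0.065 |
| 7 v 15 | 0.061 | 0.100 |
| 8 v 16 | 0.070 | 0.112 |

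Near these counts, one person can move the result across 0.05: from 7 v 16 to 7 v 15 or 8 v 16 without correction, and from 6 v 16 to 6 v 15 with it. The table does not predict how many people would be reclassified.

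**The case against.** The strongest reply is that four places agree on cotinine and one abbreviation in one sentence disagrees. The Data Analysis text is in the past tense and reports 17 participating sites, so it reads as a record of what was done. If the CO reference is a slip and cotinine was used, the quit rates are unaffected. The mailed-kit problem likewise matters only if CO really was the test and kits really were mailed.

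That is fair, and it limits what can be said about consequences. It does not reconcile the texts. If the reference is a slip, the analysis rule is misstated. If CO was used, the outcome definition is out of date and no disclosure of the change appears in the documents supplied.

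A second reply is that this is a pilot. Abstinence is a potential efficacy outcome, not a main one. The analyses are described as mainly descriptive, and the Sample Size text says that planning of the later trial will also draw on the literature. This lowers the stakes but does not remove them, since effect-size estimation is a stated use of the data.

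A third reply is that the scope question in step 3 is largely answered elsewhere, because sections 5 and 6 send every self-reported quitter for saliva validation. That is mostly right, so the point stays minor.

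Finally, a cotinine rule would still leave open how participants using nicotine replacement at 6 months are classified, although the plan records that use. This is a separate question and does not affect the contradiction.

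**Conclusion.** The concern holds. As written, the classification rule does not measure the efficacy outcome that the plan defines, and nothing in the documents reconciles the two. This must be fixed, because the rule fixes the numerators of the only between-arm comparison of cessation.

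The size and direction of any effect on the arm difference cannot be derived. They depend on whether 6-month CO readings exist, how many kits were mailed and how well the two tests agree, and the documents give none of these. The scale of 1.6 percentage points per person assumes 63 per arm. The expected counts also assume the section 11 rates, and the p-values ignore clustering. The enrolled number may differ, since the plan allows up to 150 participants.

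The documents do not show which test was actually used. The contradiction is established; an error in the reported quit rates is not.

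**What to change.** First establish which test classified participants at 6 months. Then align the texts.

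- **If cotinine was used:** replace the rule in Data Analysis with one under which a missing 6-month outcome, no saliva sample, or saliva cotinine of 15 ng/ml or more counts as not quit. The cost is one sentence, plus a reclassification if any participant was coded under the CO rule.
- **If exhaled CO was used:** amend the outcome definition in the objective and in Outcome Measures, and bring the follow-up procedure and section 6, item viii, into line. State the cut-off, how readings were taken and how participants not met in person were handled. Disclose the change, its date and its reason, and report cotinine-confirmed results alongside where samples exist. The cost is an amended definition and a disclosed change; cotinine results may not be recoverable.

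In either case, add one clause saying whether biochemical confirmation applies to both prolonged and point-prevalence abstinence.

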participant to be completed. Participants will receive a text-message reminder about the second visit at the evening. If time permits on the first day of recruitment to deliver the intervention, all aspects will be completed on that day rather than on day 2. [name], who has years of experience in training and supervising cessation trials,^{37,38,48} will be responsible for the training of PH graduate students in recruitment and conduct of the cessation trial such as 1) human subjects protection, 2) consequences of smoking, 3) motivational strategies, 4) pharmacotherapies used in smoking cessation, and 5) the study's protocol. Photographs and/or video may be taken during the sessions to be used for progress reports and presentations.

Participants in the **Usual Care** will receive up to six week supply of NRT, brochures about the QL services, and will be referred to the QL using the “fax referral form”. Participants will be informed that the QL is free, and the QL counselor will work with them to devise a specific plan to quit smoking and will arrange the delivery of free 2-week NRT for their quit attempt. Participants will have access to free NRT for a total of eight weeks (2-week supply from the QL, and 6-week supply from the study).

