Protocol for Retention - After the participant received the intervention for their assigned group, the follow-up phone calls will vary in number. In the Enhanced care, the participant will receive 4 phone calls in total. The first will be the day before the quit date and the second will be 2 weeks after the quit date to provide them with additional support. The last two phone calls will be a 3 and 6 month follow-up phone call to review their status. The Usual care will only receive 2 phone calls after their intervention. These phone calls will be placed 3 months and 6 months after their quit date to review their smoking status. If the participants fail to be contacted at any of their scheduled dates, we will proceed as follows:

Every participant will receive up to 10 phone calls to their preferred phone number. Throughout these 10 calls, voicemails will be left to remind the participant that we are trying to get in contact with them. Within the 10 phone calls, 2 text messages will be sent. One text after 5 calls and the second text after the 10 phone calls. In the text, we will encourage participant to call us back to get

STUDY PROTOCOL AND ANALYSIS PLAN

more support regardless of their smoking status. After we have completed the 2 text messages, the voicemails and the 10 phone calls, we will send a “thinking of you” letter to their house indicating that we are still interested in speaking to them to assess their progress and provide additional support at any step they may be in the process. We will stress that we are here to help them and to increase their chances of quitting smoking in the future. We will also remind them that they must keep in contact with us until the 6 month follow up to receive the additional \$30. After 2 weeks of not hearing back from the date of the card being sent, we will begin to contact their references that were written down in the baseline survey.

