STUDY PROTOCOL AND ANALYSIS PLAN

keep a record and notify the center of any potential adverse effects, illnesses, or hospitalizations. Potential risks to study participants may include:

- i. Randomization: Although it is expected that both the study treatments will be beneficial, it is possible that the treatment a participant is assigned to may later be shown to be less effective.
- ii. Nicotine Withdrawal: Smoking cessation is associated with a variety of nicotine withdrawal symptoms including: depressed mood, difficulty sleeping, irritability, anxiety, difficulty concentrating, restlessness, and increased appetite or weight gain. These symptoms are typically not severe and dissipate within a few weeks of cessation, with the exception of weight gain, which may persist for up to one year.
- iii. NRT Use: type of NRT will depend on participants' preference elicited at phase 1 (focus groups).

Nicotine Patch Use: Although most persons do not experience any major adverse effects from the nicotine patch, it is possible that a participant could experience any of the following side effects. All participants will be questioned or evaluated for these specific side effects at each session.

- a. Skin erythema, pruritus, edema, burning, and rash at the application site of the patch
- b. Dizziness, dry mouth
- c. Arthralgia, myalgia, back pain
- d. Abdominal pain, constipation, diarrhea, dyspepsia, flatulence, nausea, vomiting
- e. Impaired concentration, depression, headache, insomnia, abnormal dreams, nervousness
- f. Cough, sinusitis
- g. Allergy to nicotine
- h. Cardiovascular side effects (cardiac arrhythmia, tachycardia, vasospasm, elevated blood pressure)

Nicotine Gum Use: Although most persons do not experience any major adverse effects from the nicotine gum, it is possible that a participant could experience any of the following side effects. All participants will be questioned or evaluated for these specific side effects at each follow-up visit.

- a. Mouth soreness. Very rare; probability of occurrence is low and risk is low.
- b. Hiccups. This typically occurs through improper use of the gum. If participants report this, we work on how they are using the gum. Probability is common in those who misuse the gum; risk is low
- c. Dyspepsia. Probability and risk is low.
- d. Jaw ache. Probability and risk is low.

STUDY PROTOCOL AND ANALYSIS PLAN

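### The words that set when NRT side effects are asked about are not tied to the contact schedule, and Usual Care has no scheduled study contact between NRT supply and the 3-month call

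*Combined protocol and SAP*

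**What the plan says.** Section 6, item vi, says of side effects, adverse events and adherence: "These will all be monitored on study participants throughout the study". It gives no contact schedule.

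Section 8, item iii, sets two different rules. For the patch: "All participants will be questioned or evaluated for these specific side effects at each session". For the gum: "All participants will be questioned or evaluated for these specific side effects at each follow-up visit". One response to a reported gum effect (hiccups) is described: "If participants report this, we work on how they are using the gum".

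On supply, section 5 says of Usual Care: "Participants will have access to free NRT for a total of eight weeks (2-week supply from the QL, and 6-week supply from the study"). The paragraph on NRT gives Enhanced Care the same total.

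On contacts, section 5 gives both arms on-site contact on day 1, day 2 or both. Enhanced Care then has one counseling session, a call the day before the quit date, a call two weeks after it, and the 3- and 6-month calls. For the other arm, Protocol for Retention states: "The Usual care will only receive 2 phone calls after their intervention".

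Two starting dates are used for those calls. Protocol for Retention says of Usual Care: "These phone calls will be placed 3 months and 6 months after their quit date to review their smoking status". Follow-up and Retention says: "Participants in both arms will receive two follow-up phone calls at 3 and 6 months after enrollment to assess their smoking status". The Design paragraph also counts from enrollment.

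Section 8 separately tells every participant, in either arm, to note adverse effects and report them to the center.

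**The concern.** The protocol promises monitoring for the whole study, but the two questioning rules rest on words that the contact schedule does not define. Routine follow-up is by telephone. The only in-person follow-up is the 6-month saliva visit for self-reported quitters. The stated purposes of the calls are smoking status and quit support; none mentions side effects.

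Two things are at stake. First, section 8 lists cardiovascular effects and nicotine allergy among the possible patch effects and says all participants will be asked. If no Usual Care contact falls within the period of use, that statement rests on spontaneous reports alone during exposure, and so does the response described for gum users. Second, both arms receive the same NRT. A table of side effects by arm would naturally be read as showing what counseling adds, and unequal opportunity to be asked could produce a difference that is not real.

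**Working it through.** **Inputs from the documents**
- Supply: 6 weeks from the study plus 2 weeks from the quitline, both arms (section 5).
- Enhanced Care support calls: one day before and two weeks after the quit date (section 5).
- Usual Care calls: 3 and 6 months, counted from the quit date (Protocol for Retention) or from enrollment (Design; Follow-up and Retention).
- Eligibility requires interest in a serious quit attempt within 30 days (section 4). This suggests a range for the quit date but does not limit it.

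**Assumptions.** NRT starts on the quit date, is used without a break for the full 8 weeks, and the quitline portion arrives on time. Three months = 365.25 / 4 = 91.3, taken as 91 days.

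**Plan's own figures.** 6 + 2 = 8 weeks = 56 days of NRT. Enhanced Care calls: 2 + 2 = 4. Usual Care calls: 2. All agree with the text.

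**Gap between end of supply and the first Usual Care call**

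Timed from the quit date: gap = 91 − 56 = 35 days, whatever the quit date.

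Timed from enrollment, with quit date on day q: gap = 91 − (q + 56).

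| Quit date (day) | Supply ends (day) | Gap (days) |
|---|---|---|
| 0 | 56 | 35 |
| 14 | 70 | 21 |
| 30 | 86 | 5 |
| 35 | 91 | 0 |

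**Sensitivity**
- Timed from enrollment with a day-30 quit date, a 7-day delay in the quitline supply moves the end to day 93, past the call.
- Timed from the quit date, closing the gap takes a delay of about 35 days.
- If only the study's 6 weeks (42 days) are used, the gap is 91 − 42 = 49 days from the quit date. From enrollment it runs from 91 − 72 = 19 days (quit date day 30) to 49 days (day 0).

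**Scheduled study contacts after the quit date and within the 56 days**
- Enhanced Care: 1 (day 14 after the quit date, with 42 days of supply left).
- Usual Care: 0.

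**What the two words can mean**
- Strict reading. A session is a counseling session: Enhanced Care has one, before NRT use. A follow-up visit is in person: only self-reported quitters have one, at 6 months, in either arm. Neither arm is then asked during use.
- Broad reading. Any study contact counts. Enhanced Care then has one contact during use and Usual Care none.

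On neither reading does Usual Care have scheduled questioning during use, given the assumptions above. Only the broad reading separates the arms.

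**The case against.** The strongest reply is that this is a matter of loose wording. Much of it stands:

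- A reader might infer that Usual Care has no sessions or visits at all. It does: the on-site contact at which its assigned care is given, and the 6-month saliva visit for self-reported quitters. The payment text for the first treatment session names no arm.
- Section 6, item vii, refers to follow-up visits when it describes tracking of other cessation treatment, and section 5 places the corresponding questions at recruitment and at 3 and 6 months. This supports reading follow-up visit as the calls both arms share. The gum rule would then be equal between arms, though it would still fall after supply ends under the assumptions above.
- A reader might infer that Enhanced Care is asked during use and so will record more side effects. No section says so. The two-week call is described as reviewing progress and relapse-prevention skills. The documents show unequal opportunity, not unequal questioning.
- A reader might conclude that problems in Usual Care surface too late to act on. That holds at most for scheduled questioning. Both arms receive side-effect information and instructions for use, both are told to report problems to the center, and item vi passes reports to the investigators.
- Side effects are not among the main, efficacy or secondary outcomes in section 7, and Data Analysis plans no between-arm comparison of them.

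What the reply does not remove is that two undefined terms carry the questioning rule, the calls have two starting dates, and Usual Care has an interval without scheduled study contact that covers the assumed period of NRT use. Quitline counselors may speak to participants in that interval, but the documents describe no route from the quitline to the study for side-effect reports.

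**Conclusion.** The concern holds as a gap between the monitoring statement and the contact schedule. With continuous use from the quit date, the first scheduled Usual Care contact after supply comes about 35 days after the NRT ends (quit-date timing) or about 5 to 35 days after (enrollment timing, quit dates day 0 to 30). Quit dates after about day 35 close the gap under enrollment timing; delayed quitline supply or intermittent use can do so under either timing.

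The monitoring statement in section 6 is therefore not supported by scheduled questioning in Usual Care during use, and any by-arm tabulation of side effects may be biased toward more reports in Enhanced Care. It is tempting to put a size on that bias. The documents give no side-effect, elicitation or recall rates, so none can be stated. No planned efficacy analysis, sample size or power figure is touched.

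**What to change.** 1. Reconcile section 5 (Design, the arm descriptions and NRT paragraph, Follow-up and Retention, Protocol for Retention), section 6 item vi and section 8 item iii. State at which contacts side effects are asked, for each arm and each NRT form, and give one date from which the 3- and 6-month calls are timed.
2. Use the same side-effect checklist for patch and gum users at the 3- and 6-month calls in both arms, worded to cover the whole NRT course.
3. Base any by-arm side-effect table on those common contacts plus spontaneous reports. List events elicited at the two Enhanced-only calls separately.
4. Either support the section 6 monitoring statement equally in both arms, by a means the sponsor chooses, or limit the statement to what is scheduled.

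The cost is protocol wording and one checklist added to calls already planned. The checklist makes the arms comparable but does not make reporting prompt: at 3 months it will usually rely on recall. Whether to add a contact during the supply period is for the sponsor to decide.
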